## 5.2 Safety Evaluation

During the sleep study, arterial oxygen saturation using pulse oximetry, transcutaneous carbon dioxide tension, EEG and EKG will be continuously monitored, and the patient will be visualized via a video camera.

During CBF measurements with ventilatory responses, heart rate, pulse oximetry, transcutaneous carbon dioxide tension, and end-tidal CO2 measurements will be continuously monitored and the patient will be directly visualized. A physician will be present whenever CO2 is administered.

---

## 6 STATISTICAL CONSIDERATIONS

### 6.1 Primary Endpoint

The primary endpoint is the cerebral blood flow change in OSAS subjects compared to controls during hypercapneic challenge and its correlation with behavioral and cognitive testing results.

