## PROTOCOL SYNOPSIS

---

Study Title	Cerebral blood flow and neurocognition in children with obstructive sleep apnea
Funder	National Heart, Lung, and Blood Institute (NHLBI)
Study Rationale	
The rationale of this case-control study is to identify the mechanisms of neurocognitive dysfunction in children with the obstructive sleep apnea syndrome (OSAS). OSAS is common. It occurs in 2-3% of children and if left untreated, is associated with important complications such as hypertension, endothelial dysfunction, and cognitive and behavioral impairment. This is important as children's brains are developing and thus, the long-term consequences of cognitive and behavioral dysfunction may have great impact on their adult life. Imaging studies of adults with OSAS have identified abnormal morphology of the frontal cortex, an important area for executive function. Other studies using magnetic resonance spectroscopy imaging (MRSI) have shown altered central nervous system metabolites of neuronal white and gray matter in adult and children with OSAS, which may be indicative of neuronal injury. Researchers have hypothesized that this neuronal injury results in cognitive and behavioral consequences, and is caused by OSAS-associated hypoxemia. OSAS, however, is not only characterized by periods of hypoxemia. OSAS patients experience hypercapnia and frequent arousals from sleep as well, as a consequence of the repetitive episodes of upper airway obstruction that are the hallmark of OSAS. This study will further identify the mechanisms of behavioral and cognitive dysfunction in children with OSAS by measuring cerebral blood flow changes in children with OSAS, and controls during hypercapneic challenges during wakefulness and correlating these results with measures of cognition and behavior. In addition, all participants will be retested over 1 year approximately to evaluate changes in behavior, cognition and cerebral blood flow related to treatment of OSAS vs. development.

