Study Objective(s)	
Primary
 
 
• To determine the changes in cerebral blood flow in children with OSAS and controls measured by near-infrared spectroscopy during wakefulness and sleep, elicited by hypercapneic challenge.
 
 
Secondary
 
 
• To determine the correlation between changes in cerebral blood flow in children with OSAS and controls measured by the aforementioned testing, and cognitive and behavioral measures
 

---

- To determine the changes in cerebral blood flow in children with OSAS, measured by near-infrared spectroscopy during wakefulness and sleep, elicited by hypercapneic challenge after clinically indicated surgical treatment of OSAS.
- To determine longitudinal changes in cerebral blood flow in controls, measured by near-infrared spectroscopy during wakefulness and sleep, elicited by hypercapneic challenge over one year.
- To determine the correlation between changes in cerebral blood flow in children with OSAS after treatment of OSAS measured by the aforementioned testing, and cognitive and behavioral measures.

Study Design	Case-control study
Subject Population	Inclusion Criteria (OSAS Subjects)
key criteria for Inclusion and Exclusion:	
 
1. Subjects age 6-12 years
 
2. Absence of neurologic, cardiovascular, pulmonary or any other chronic illness.
 
3. No prior surgery on the nose, palate or oropharynx
 
4. No current drug intake that may interfere with testing such as sedatives or stimulants
 
5. No prior treatment of sleep-disordered breathing.
 
6. Polysomnographic recording criteria: subjects with OSAS must have an obstructive apnea hypopnea index (AHI) <math>\geq 5/\text{hour}</math>.
 
7. Parent/guardian permission (informed consent) and if appropriate, child assent.
 

	Exclusion Criteria (OSAS Subjects)
	
 
1. Previous adenotonsillectomy
 
2. Previous use of CPAP
 
3. Craniofacial anomalies
 
4. Genetic syndromes (e.g. Trisomy 21, Prader-Willi)
 
5. ADHD on medication
 
6. Developmental delay as determined by receiving a score <math><70</math> on the ABAS-III
 
7. Non-English speakers due to the nature of neurocognitive testing
 

	Inclusion Criteria (Control Subjects)

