#### **Exclusion Criteria (Control Subjects)**

1. Previous adenotonsillectomy
2. Previous use of CPAP
3. Craniofacial anomalies
4. Genetic syndromes (e.g. Trisomy 21, Prader-Willi)
5. ADHD on medication
6. Developmental delay as determined by receiving a score  $<70$  on the ABAS-III
7. Positive Pediatric Sleep Questionnaire.
8. Non-English speakers due to the nature of neurocognitive testing

---

Number Of Subjects	70 controls, 70 subjects with OSAS. Single site: CHOP.
---------------------------	--

---

Study Duration	Each subject's participation will last 12-14 months approximately.
-----------------------	--

---

Study Phases	(1) Screening: screening for eligibility and obtaining consent
Screening	(2) Observation Period: measurements made for monitoring control
Study Treatment	and OSAS participants over time.
Follow-Up	
Efficacy Evaluations	Changes in cerebral blood flow
Safety Evaluations	Vital signs will be monitored throughout testing.
Statistical And Analytic Plan	A sample size of 50 in each group (total N = 100) will have 80% power to detect a moderate CBF changes effect size of 0.566 using a two group t-test with a 0.05 two-sided significance level. We plan to recruit 70 in each group to account for attrition.
DATA AND SAFETY MONITORING PLAN	Independent medical monitor and DSMB (both mandated by NHLBI)

---

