### **2.1 Primary Objective (or Aim)**

The primary objectives of this study are:

- To determine whether children with OSAS have impaired cerebral blood flow regulation elicited by hypercapneic challenge compared to normal controls, and whether this impairment correlates with cognitive and behavioral measurements.

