#### 6.4.2 Analysis of Primary Outcome of Interest

The primary analysis will include all subjects meeting all inclusion and exclusion criteria and completing all study visits.

The primary endpoint will be the change in CBF in OSAS and controls at baseline.

The secondary endpoint will be the change in CBF in OSAS and controls at 6 and 12 months after baseline measurements for controls and after adenotonsillectomy for OSAS.

Longitudinal models using generalized estimating equations (GEE) will be fitted to explore effects of treatment on CBF and NBT. An indicator variable for treatment, time, and a time by treatment group interaction term will be included in the models. If the interaction term

---

differs significantly from zero, this will indicate that the change over time in the outcome of interest differs significantly between the two groups. We will assess the sensitivity of results to the choice of working correlation structure that models association in the GEE analyses. We will also implement quasi-least squares (QLS), an approach based on GEE that allows for implementation of the Markov correlation structure.(32) The Markov structure is plausible if participants have unequal temporal spacing of their measurements. In addition, we will consider the application of mixed effects models if the assumptions of these models are met. An indicator variable for subjects who resolve after treatment versus those who do not resolve after treatment will be included in the model to account for those children whose OSAS may not resolve after surgery.(22, 33, 34) Pre-, post treatment change in AHI will be included in the model, and potential confounding variables such as age, gender, race, socio-economic status and BMI will also be included in the models.

Hypercapnic ventilatory responses will be controlled for BMI as obese participants may have different responses compared to non-obese participants.

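### The CBF–cognition correlation is primary in Sections 2.1 and 6.1 but not in the Synopsis or 6.4.2, and no section names the state or hemisphere of the CBF contrast that 6.5 is meant to power

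*Combined protocol and SAP*

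**What the plan says.** **Status of the correlation.** Section 2.1 asks, as the primary objective, whether CBF regulation is impaired in OSAS "and whether this impairment correlates with cognitive and behavioral measurements". Section 6.1 takes this into the primary endpoint: the CBF change in the OSAS group "compared to controls during hypercapneic challenge and its correlation with behavioral and cognitive testing results". The Synopsis instead lists among its secondary objectives "To determine the correlation between changes in cerebral blood flow in children with OSAS and controls measured by the aforementioned testing" and the cognitive and behavioral measures. Section 6.4.2 leaves the correlation out: "The primary endpoint will be the change in CBF in OSAS and controls at baseline". Section 6.2 does not list it as a secondary endpoint.

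**The CBF variable.** The Synopsis primary objective is about CBF changes "in children with OSAS and controls measured by near-infrared spectroscopy during wakefulness and sleep". The Synopsis rationale describes measuring them in children with OSAS "and controls during hypercapneic challenges during wakefulness and correlating these results with measures of cognition and behavior", so it mentions wakefulness only. Sections 2.1, 6.1, 6.4.2 and 6.5 name no state, sleep stage or hemisphere. Section 5.1.3 averages each hemisphere separately and passes both right and left CBF to the analysis. It gives slow-wave sleep priority for the sleep challenges, with stage 2 and REM added when possible.

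**Power.** The Synopsis states that 50 per group give "80% power to detect a moderate CBF changes effect size of 0.566 using a two group t-test" at two-sided 0.05. Section 6.5 repeats the figures without mentioning CBF. Neither gives power for a correlation.

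**The concern.** A primary endpoint should tell a reader, before any data are seen, which single result answers the main question. Here the current sections disagree on whether the correlation belongs to it. Even the narrowest version, in 6.4.2, could be met by the waking or the sleeping response, on the left or the right. The correlation could be computed with any of seven instruments given at the testing visits (ABAS-III is listed as well, but is scheduled at screening), in the OSAS group or in both groups pooled.

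The stated error rate and power belong to one comparison. If several could each count as success, the chance of a false positive exceeds 5%. If several must all succeed, error does not inflate but power falls below the stated 80%. The plan does not say which applies.

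**Working it through.** **Inputs from the documents.** Section 6.5: n = 50 per group, effect size d = 0.566, two-sided alpha 0.05, two-group t-test. Section 6.4.2 restricts the primary analysis to subjects "completing all study visits", so 50 evaluable per group is the right base, not the 70 recruited.

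**Inputs assumed.** The documents give no between-measure correlations. I take left–right 0.6 to 0.9, wake–sleep 0.2 to 0.6 and, where power is computed, d = 0.566 in both states.

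**1. The plan's own figure.** Noncentrality = d × √(n/2) = 0.566 × √25 = 2.83, on 98 degrees of freedom. Power at two-sided 0.05 = 80.0%; required n = 49.98. The stated figure reproduces. Recruitment is consistent: 50/70 = 71.4% retained, an implied loss of 28.6%.

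**2. Any of several CBF contrasts may count, each at 0.05.** If independent, the rate is 1 − 0.95^k.

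| Contrasts | Independent | Assumed correlations (simulated) |
|---|---|---|
| 4 (2 states × 2 hemispheres) | 1 − 0.95⁴ = 18.5% | about 12–17% |
| 2 (wake or sleep, hemispheres averaged) | 1 − 0.95² = 9.75% | 9–10% |

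**3. Both states must succeed, each at 0.05.** If independent, 0.80 × 0.80 = 64%. At wake–sleep correlation 0.2 to 0.6, joint power is 66% to 70%.

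**4. Either state may succeed, each at 0.025.** Power per comparison is 71.0% at 50 per group. Power for at least one is about 89% at wake–sleep correlation 0.2 and 84% at 0.6. Simulating t statistics instead of normal ones gives 89.3% and 83.4%, so the lower end is good to about one point. To restore 80% per comparison, 61 evaluable per group are needed; 61 × 70/50 = 85.4, so 86 recruited.

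**5. The correlation as a primary component.** Using Fisher's z at two-sided 0.05, 80% power requires r of about 0.39 with the 50 OSAS children alone, or 0.28 with 100 pooled. At an assumed r = 0.3, power is 56% (N = 50) or 86% (N = 100). If one named correlation and one fixed CBF contrast must both be significant and are independent, joint power is 0.80 × 0.56 = 45% or 0.80 × 0.86 = 69%. It cannot exceed the weaker test, so the ceilings are 56% and 80%. If any of seven instruments may supply the correlation unadjusted, the false-positive rate for that component is 1 − 0.95⁷ = 30% if independent, and 23% at inter-instrument correlation 0.5.

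**The case against.** **The plan can be read as settled.** Section 6.4.2 is the analysis section, and with the Synopsis power statement it points to one baseline OSAS–control comparison of CBF. That is the most natural reading. It still conflicts with 6.1 in the same chapter, and it names neither state nor hemisphere.

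**Sleep stage is not wholly open.** This stands in part. Section 5.1.3 gives slow-wave sleep priority, so treating all stages as equal candidates would overstate the problem. But that is an order for conducting challenges, not a choice of analysis variable, and it does not decide between wake and sleep.

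**No error rate is shown to be exceeded.** This stands. A reader might infer that the study's type I error is inflated. Every inflation figure above needs a rule that any contrast may count, and the documents contain no such rule. They contain no all-must-succeed rule either.

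**Wakefulness might look like the intended primary state.** The rationale sentence suggests it, but the Synopsis primary objective, the Abstract, Section 1.1 and Section 3.1 all name wakefulness and sleep. The Abstract and 1.1 report the waking response as already found blunted, and the Abstract calls the sleep response unknown. The documents do not support choosing for the investigators.

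**Naming state and hemisphere does not guarantee 80%.** This also stands. No section links 0.566 to a particular CBF variable or says how the response is computed. Section 6.4.2 does not name a t-test for the primary comparison; the models it describes are longitudinal.

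**Conclusion.** The point holds as a contradiction between current sections and an incompletely defined primary variable. Sections 2.1 and 6.1 make the correlation primary; the Synopsis and 6.4.2 do not. The state and hemisphere of the CBF contrast are unnamed, and the analysis stage is unnamed despite the operational priority for slow-wave sleep.

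The sample-size arithmetic is correct, so this is not a finding that the study is too small. The stated level and power simply cover one contrast. The consequences are conditional: about 12–17% false positives if any of four contrasts may count, 9–10% for wake or sleep, and 66–70% power if both states must succeed. All rest on the assumed correlations, and the last also on d = 0.566 in each state. The change should be made before the data are analysed; confidence in the contradiction itself is high.

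**What to change.** Put one identical primary-endpoint sentence in the Synopsis, 2.1, 6.1 and 6.4.2: the baseline OSAS–control difference in CBF response to hypercapnia, in one state chosen by the investigators (and one stage if sleep is chosen, where slow-wave is already the operational priority), under one hemisphere rule such as the left–right mean, tested at two-sided 0.05. The same sentence should say how the response is computed.

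Make the cognition correlations, the other state, the other stages and the separate hemispheres secondary, with Holm adjustment or an exploratory label, and list the correlations in 6.2. Tie 6.5 to the named contrast. The 50 per group and 80% are then arithmetically correct, provided the assumed 0.566 applies to that variable.

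If wake and sleep both stay primary, state the success rule:

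- **Either may succeed:** test each at 0.025. Report per-comparison power (71% at 50 per group) and power for at least one (about 84–89%), with the assumptions.
- **Both must succeed:** test each at 0.05. Report joint power with its assumed correlation.

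**Cost.** With one named contrast, wording only: no new data and no change in recruitment. Recruitment changes only if both states stay primary and 80% power is wanted for each comparison or jointly. The scientific cost is that the correlation and the state not chosen lose primary status. If wakefulness is chosen, that includes the sleep response the Abstract calls unknown.

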### 6.2 Secondary Endpoints

Secondary endpoints will include the following:

- The change in cerebral blood flow regulation in OSAS subjects before and after treatment of OSAS at 6 months
- The change in behavioral and cognitive testing results before and after treatment of OSAS at 6 and 12 months
- The association between cerebral blood flow regulation and severity of OSAS at baseline and its changes at 12 months.

### 6.3 Control of Bias and Confounding

The co-investigator performing the neurocognitive testing will be blinded to the subjects' condition (OSAS or controls).

### 6.4 Statistical Methods

#### 6.4.1 Baseline Data

Descriptive analyses will consist of frequencies for categorical variables, mean, median, range, standard deviation (SD), standard error of the mean (SEM) for continuous variables, and 95% CI of the means and of the medians (for skewed distributions). Demographic variables will be compared between groups at baseline using the t-test or Wilcoxon rank sum test (for continuous variables) or the X test (for categorical variables). The distributions of outcomes will be assessed via graphical checks and tests for normality. If necessary, transformations (e.g., log) will be applied to improve normality and skewed data.

#### 6.4.2 Analysis of Primary Outcome of Interest

The primary analysis will include all subjects meeting all inclusion and exclusion criteria and completing all study visits.

The primary endpoint will be the change in CBF in OSAS and controls at baseline.

The secondary endpoint will be the change in CBF in OSAS and controls at 6 and 12 months after baseline measurements for controls and after adenotonsillectomy for OSAS.

Longitudinal models using generalized estimating equations (GEE) will be fitted to explore effects of treatment on CBF and NBT. An indicator variable for treatment, time, and a time by treatment group interaction term will be included in the models. If the interaction term

---

differs significantly from zero, this will indicate that the change over time in the outcome of interest differs significantly between the two groups. We will assess the sensitivity of results to the choice of working correlation structure that models association in the GEE analyses. We will also implement quasi-least squares (QLS), an approach based on GEE that allows for implementation of the Markov correlation structure.(32) The Markov structure is plausible if participants have unequal temporal spacing of their measurements. In addition, we will consider the application of mixed effects models if the assumptions of these models are met. An indicator variable for subjects who resolve after treatment versus those who do not resolve after treatment will be included in the model to account for those children whose OSAS may not resolve after surgery.(22, 33, 34) Pre-, post treatment change in AHI will be included in the model, and potential confounding variables such as age, gender, race, socio-economic status and BMI will also be included in the models.

Hypercapnic ventilatory responses will be controlled for BMI as obese participants may have different responses compared to non-obese participants.

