### **3.2 Study Duration, Enrollment and Number of Sites**

Duration of study participation for the subject will be 12-14 months approximately.

---

We plan to enroll 70 subjects in each arm in order to have 50 evaluable subjects in each arm at the end of the study. This research will be carried out at one site only: Children's Hospital of Philadelphia.

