### **3.3 Total Number of Study Sites/Total Number of Subjects Projected**

#### **3.3.1 Duration of Study Participation**

##### **3.3.1.1 Subjects with OSAS**

The study duration is estimated at 12-14 months approximately. However, this will depend on the timing of treatment as they will undergo testing pre- and post-OSAS treatment. Their participation will entail a total of 8 visits:

Pre-treatment: The cognitive and behavioral, and CBF during wakefulness testing duration is one full day. The CBF nighttime testing is one full night.

Post-treatment: Six to twelve weeks after clinically indicated surgical treatment, OSAS participants will have a repeat baseline polysomnogram (one full night) to assess for residual OSA. Six and twelve months after the surgical treatment, the sleep study with the nighttime CBF testing, as well as the daytime neurobehavioral and CBF testing will be repeated to assess for changes.

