##### **3.3.1.2 Control Subjects**

The study will include 7 total visits for controls: a baseline sleep study to ensure normalcy, three full days of cognitive and behavioral and CBF testing (baseline, 6 and 12 months), and three sleep studies with CBF testing (baseline, 6 and 12 months). A daytime visit and one night time visit may be scheduled during a 24-hour period if the participant and family wish so. Otherwise, they will be scheduled on separate days.

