#### 4.1.3 Visit 3: Post-Operative sleep study 6-12 weeks after adenotonsillectomy

- Sleep study to assess resolution of OSAS. If the post-operative AHI is  $\geq 5$  events per hour, participants will be referred to clinical care. However, they will continue in the study and perform procedures as planned. Data collected from such participants will be analyzed separately.
- Height and weight assessment.

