**4.5 Subject Completion/Withdrawal**

Subjects may withdraw from the study at any time without prejudice to their care. They may also be discontinued from the study at the discretion of the Investigator for lack of adherence to study treatment or visit schedules, AEs, or due to inability to follow instructions and perform testing. The Investigator or the Sponsor (if applicable) may also withdraw subjects who violate the study plan, or to protect the subject for reasons of safety or for administrative reasons. It will be documented whether or not each subject completes the clinical study. If the Investigator becomes aware of any serious, related adverse events after the subject completes or withdraws from the study, they will be recorded in the source documents and on the CRF.

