## **6.5 Sample Size and Power**

A sample size of 50 in each group (total N = 100) will have 80% power to detect a moderate effect size of 0.566 using a two group t-test with a 0.05 two-sided significance level. We plan to recruit 70 in each group to account for attrition.

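### The primary endpoint is measured at baseline, but its analysis keeps only children who complete every visit to 12 months; at planned attrition this discards up to 29% of valid baseline data and selects on later events

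*Combined protocol and SAP*

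**What the plan says.** Section 6.4.2 gives the analysis set first: "The primary analysis will include all subjects meeting all inclusion and exclusion criteria and completing all study visits". The endpoint follows at once: "The primary endpoint will be the change in CBF in OSAS and controls at baseline". The 6- and 12-month CBF changes are assigned to the secondary endpoint in the same section.

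On numbers, section 3.2 enrols 70 per arm "in order to have 50 evaluable subjects in each arm at the end of the study", and section 6.5 says: "We plan to recruit 70 in each group to account for attrition". Section 6.5 bases its 80% power on 50 per group.

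On visits, section 3.3.1.1 says of OSAS children: "Their participation will entail a total of 8 visits". Section 3.3.1.2 says: "The study will include 7 total visits for controls". Only the OSAS group has the post-operative Visit 3 (section 4.1.3): "Sleep study to assess resolution of OSAS".

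Section 4.5 also lets the investigator discontinue children "for lack of adherence to study treatment or visit schedules, AEs, or due to inability to follow instructions and perform testing".

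The plan gives no other analysis set for the baseline comparison, no sensitivity analysis using all baseline tests and no rule for missing data. Section 6.3, on control of bias, covers only blinding of the neurocognitive tester.

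**The concern.** Once a baseline CBF test has been obtained, nothing that happens later can make it missing. Later losses shrink the baseline sample only because the rule removes those children. Two costs follow.

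- **Precision.** Valid measurements of the primary endpoint are set aside with nothing gained in return.
- **Selection.** The OSAS-control comparison is not randomised, and the rule conditions it on events after the endpoint was measured. Those events differ by group: OSAS follow-up visits are timed from adenotonsillectomy, so an OSAS child who does not have surgery cannot be a completer, whereas controls face no such condition. If completion is related to baseline CBF response differently in the two groups, the estimated baseline difference is biased.

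The point concerns the baseline primary comparison only. The plan states no completer rule for the GEE, quasi-least squares or mixed models.

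**Working it through.** **Inputs.** 50 evaluable and 70 enrolled per group (sections 3.2, 3.3.2, 6.5); standardised effect d = 0.566, two-group t-test, two-sided alpha 0.05 (section 6.5); visit schedule (Tables 1 and 2, sections 4.1 and 4.2). The documents do not say when the losses are expected.

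**1. When the endpoint is complete, and what must follow**

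| | Baseline CBF complete by | Later visits needed to count as a completer |
|---|---|---|
| OSAS | Visit 2 (sleep at Visit 1, awake at Visit 2) | Visits 3 to 7 = 5, all timed from surgery |
| Controls | Visit 3 (awake at Visit 2, sleep at Visit 3) | Visits 4 to 7 = 4 |

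**2. The plan's own figure.** Power is the probability that a noncentral t variable with 2n − 2 degrees of freedom and noncentrality d·√(n/2) falls outside the two-sided 5% critical values. At n = 50 the noncentrality is 0.566 × √25 = 2.83 and power is 80.0%. The stated 80% reproduces. Planned loss is (70 − 50)/70 = 28.6% per group.

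**3. Cost of the rule.** Let n be the number per group with a valid baseline test, of whom 50 complete. Early losses are 70 − n, the share of valid data discarded is (n − 50)/n, and the standard error using all n, relative to completers only, is √(50/n).

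| n with valid baseline | Early losses | Discarded by the rule | Power at 0.566 using all n | Effect detectable with 80% power | SE ratio |
|---|---|---|---|---|---|
| 50 | 20 | 0% | 80.0% | 0.566 | 1.000 |
| 55 | 15 | 5/55 = 9.1% | 83.7% | 0.539 | 0.953 |
| 60 | 10 | 10/60 = 16.7% | 86.8% | 0.516 | 0.913 |
| 65 | 5 | 15/65 = 23.1% | 89.3% | 0.495 | 0.877 |
| 70 | 0 | 20/70 = 28.6% | 91.4% | 0.477 | 0.845 |

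From 55 to 70 per group, the confidence interval is about 5% to 15% narrower than with 50.

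**4. Possible bias (illustration only; the correlations are assumed).** Suppose completion is related to baseline CBF response in one group only, with retained fraction p = 50/n.

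- Latent-normal completion variable with correlation ρ: the group mean shifts by ρ·φ(z)/p SD, where φ is the normal density at the completion cut-off z. For ρ = 0.1 to 0.3 this is 0.05 to 0.14 SD at 28.6% loss and 0.02 to 0.05 SD at 9.1% loss.
- Correlation r with binary completion: the shift is r·√((1 − p)/p) SD. For r = 0.1 to 0.3 this is 0.063 to 0.190 SD at 28.6% loss and 0.032 to 0.095 SD at 9.1% loss.

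**The case against.** The strongest reply has five parts.

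1. **The study is powered on 50 per group, so there is no power error.** This is correct and stands. But meeting the power target is no reason to discard valid endpoint data, and enrolling more children does not remove selection.

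2. **The completer sentence may have been meant for the longitudinal models.** Section 6.4.2 names no test for the baseline comparison, and section 6.1 gives the primary endpoint no time point. That is possible, but the text applies the rule to the primary analysis and sets that endpoint at baseline. If the intent was different, the wording still has to change. GEE and mixed models do not need complete cases either.

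3. **An unrestricted GEE would already give a baseline contrast from all available data.** In part. However, the model described includes resolution after surgery and pre- to post-treatment AHI change, which need post-operative data. It is not a clean substitute.

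4. **29% is an extreme.** Some losses may precede a usable baseline test: failed screening after consent, wake tests discarded under section 5.1.3, or poor NIRS recordings (section 4.4). This stands, which is why the share is shown from 0% to 28.6%. Nor is 28.6% a hard ceiling, since actual attrition could exceed the plan.

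5. **The bias is unproven, and similar selection in both groups would partly or wholly cancel.** This also stands. The loss of precision does not depend on any bias assumption.

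It is also fair to say that a valid baseline test needs defining, because usable awake and sleep tests may differ in number. That affects how the remedy is worded, not whether it is needed.

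**Conclusion.** The concern holds. As written, who enters the baseline comparison depends on surgery and on attendance for up to a year after the endpoint was measured, and nothing else in the plan provides a baseline analysis free of that condition.

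The demonstrable cost is precision. If 55 to 70 children per group have a valid baseline test and 50 complete, the rule gives up about 4 to 11 percentage points of power at 0.566 (83.7 − 80.0 = 3.7; 91.4 − 80.0 = 11.4). If all 20 planned losses per group come before the baseline test, nothing is lost. These figures assume that attrition matches the plan.

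Selection bias is possible, but its direction and size cannot be derived from the documents. The matter should be fixed; it does not invalidate the study.

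**What to change.** - **Section 6.4.2:** define the primary analysis set as all eligible participants with a valid baseline CBF test, regardless of later surgery, withdrawal or missed visits. Apply the definition separately to the awake and sleep tests. Keep the completer set as a sensitivity analysis of the baseline comparison.
- **Section 6.5:** keep 80% power at 50 per group as the minimum. Add one sentence stating that power for the baseline comparison at d = 0.566 would be about 84% to 91% with 55 to 70 usable baseline tests per group (detectable effect 0.54 to 0.48).

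The cost is a reworded analysis set and one added sentence, with no extra patients, visits or data.
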